7.4.2 Definitions of Dose Limiting Toxicities (DLT)

A DLT will be defined as any Grade 3 or higher treatment-related toxicity that occurs during the DLT observation phase (8 weeks post Y90-RE), including:

- Any event resulting in a delay of cycle 2 by \geq 14 calendar days
- Any Grade 4 immune related adverse event (irAE)
- Any Grade 3 immune related AE (irAE) that does not resolve to \leq Grade 1 or to baseline with immunosuppressive therapy within 3 weeks
- Any Grade 3 colitis
- Any Grade 3 noninfectious pneumonitis irrespective of duration
- Grade 4 neutrophil count decreased lasting longer than 5 calendar days
- Grade 4 platelet count decreased
- Grade 3 platelet count decreased with hemorrhage
- Any \geq Grade 2 pneumonitis that does not resolve to \leq Grade 1 within 7 days of the initiation of maximal supportive care
- Any other Grade 3 irAE (excluding colitis or pneumonitis), that does not downgrade to Grade 2 within 7 days after onset of the event despite optimal medical management including systemic corticosteroids or does not downgrade to \leq Grade 1 or baseline within 14 days
- Liver transaminase elevation $> 8 \times$ ULN
- Total bilirubin $> 5 \times$ ULN
- AST or ALT $> 5-8 \times$ ULN with concurrent increase in total bilirubin $> 2 \times$ ULN without evidence of cholestasis or alternative explanations, e.g., viral hepatitis, disease progression in the liver, etc. (Hyll's Law). Exception: If it is present at cycle 3 but resolves at cycle 4 it is not a DLT.
- Any \geq grade 3 non-hematologic toxicity, except:
 - Grade 3 nausea or vomiting that lasts < 48 hours and resolves to \leq Grade 1 either spontaneously or with conventional medical intervention
 - Grade 3 nausea, vomiting, and diarrhea lasting < 72 hours in the absence of maximal medical therapy
 - Grade 4 vomiting and diarrhea lasting < 72 hours in the absence of maximal medical therapy
 - Grade 3 hypertension in the absence of maximal medical therapy
 - Grade 3 metabolic abnormalities (e.g. hypokalemia, hypomagnesemia, hypocalcemia, hypophosphatemia) that recover to \leq Grade 1 within 48 hours
 - \geq Grade 3 electrolyte abnormality lasting < 72 hours, is not clinically complicated, and resolves spontaneously or responds to conventional medical intervention.
 - Grade 3 or 4 elevation in serum amylase and/or lipase that are not associated with clinical or radiographic evidence of pancreatitis.
 - Grade 3 rash < 5 calendar days

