 - Grade 3 rash that resolves to \leq Grade 1 within 3 weeks
 - Grade 3 fatigue lasting ≤ 7 days
 - Grade 3 endocrine disorder (thyroid, pituitary, and/or adrenal insufficiency) that is managed with or without systemic corticosteroid therapy and/or hormone replacement therapy and the subject is asymptomatic

- Grade 3 inflammatory reaction attributed to a local antitumor response (e.g., inflammatory reaction at sites of metastatic disease, lymph nodes)
- Concurrent vitiligo or alopecia of any AE grade
- Grade 3 infusion-related reaction (first occurrence and in the absence of steroid prophylaxis) that resolves within 6 hours with appropriate clinical management
- Grade 3 or 4 neutropenia that is not associated with fever or systemic infection that improves by at least 1 grade within 7 days. Grade 3 or Grade 4 febrile neutropenia will be a DLT regardless of duration or reversibility

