8.0 Dosage Modification Based on Adverse Events (details tabulated in appendix VIII)

Strictly follow the modifications in this table for the first **two** cycles, until individual treatment tolerance can be ascertained. Thereafter, these modifications should be regarded as guidelines to produce mild-to-moderate, but not debilitating, side effects.

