8.1 Treatment schedule modifications in patients based on adverse events

Patients will be evaluated by the study team prior to each dose of durvalumab for an adverse event check. Determination will be made if the adverse event is treatment-related (possible, probable or definite), i.e. a toxicity (see Section 10; Adverse event monitoring and reporting). If any adverse event has occurred, then the treatment schedule will be modified as in Section 8.2.

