8.2 Treatment schedule modifications for durvalumab

Adverse events (both non-serious and serious) associated with durvalumab exposure may represent an immunologic etiology. These adverse events may occur shortly after the first dose or several months after the last dose of treatment. Durvalumab must be withheld for drug-related toxicities and severe or life-threatening AEs per Table 8.21 below. See Section 9.0 for supportive care guidelines, including use of corticosteroids.

Table 8.21 Dose Modification Guidelines for Drug-Related Adverse Events for Durvalumab			
CTCAE System/Organ/Class	Adverse Event	Grade	Action
Gastrointestinal disorders	Diarrhea or Colitis	2	Hold all protocol treatment until Grade 0-1. If AE does not resolve to Grade 0-1 within 2 weeks, then permanently discontinue all protocol treatment
		3, 4	Permanently discontinue all protocol treatment
Investigations	Alanine aminotransferase increased, Aspartate aminotransferase increased, and blood bilirubin increased	2	Hold all protocol treatment until Grade 0-1. If AE does not resolve to Grade 0-1 within 2 weeks, then permanently discontinue all protocol treatment
		3-4	Permanently discontinue all protocol treatment
Metabolism and nutrition disorders	Glucose intolerance (Type 1 diabetes mellitus [if new onset]) or Hyperglycemia	T1DM or 2-4	Hold all protocol treatment until clinically and metabolically stable.

Table 8.21 Dose Modification Guidelines for Drug-Related Adverse Events for Durvalumab

CTCAE System/Organ/Class	Adverse Event	Grade	Action	
Endocrine disorders	Endocrine disorders-Other, specify: Hypophysitis	2-4	Hold all protocol treatment until Grade 0-1. If AE does not resolve to Grade 0-1 within 2 weeks, then permanently discontinue all protocol treatment	
	Hypothyroidism	2-4	Therapy with durvalumab can be continued while thyroid replacement therapy is instituted	
	Hyperthyroidism	2-3	Hold all protocol treatment until Grade 0-1. If AE does not resolve to Grade 0-1 within 2 weeks, then permanently discontinue all protocol treatment	
		4	Permanently discontinue all protocol treatment	
General disorders and administration site conditions	Infusion related reaction	1, 2	Follow infusion related reaction treatment guidelines (Table 9.21). Hold all protocol treatment until Grade 0-1. If AE does not resolve to Grade 0-1 within 2 weeks, then permanently discontinue all protocol treatment	

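### DLT and re-dosing rules need one answer each for 6–7-day afebrile Grade 4 neutropenia, liver rises that clear between cycles 3 and 4, and Grade 3 diarrhea/colitis or liver tests

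*Combined protocol and SAP*

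**What the plan says.** **DLT definition (Section 7.4.2).** The lead sentence is broad: "A DLT will be defined as any Grade 3 or higher treatment-related toxicity" in the 8 weeks after Y90-RE. Specific items follow, then a catch-all for any event of at least "grade 3 non-hematologic toxicity, except" for a list of exclusions.

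- Neutropenia appears twice. One item counts "Grade 4 neutrophil count decreased lasting longer than 5 calendar days". An exclusion placed in the non-hematologic list exempts "Grade 3 or 4 neutropenia that is not associated with fever or systemic infection that improves by at least 1 grade within 7 days". Febrile Grade 3 or 4 neutropenia always counts.
- Liver tests have three items: transaminases above 8x ULN; bilirubin above 5x ULN; and AST/ALT above 5–8x with bilirubin above 2x ULN without cholestasis or another explanation. Only the third carries a timing clause: "Exception: If it is present at cycle 3 but resolves at cycle 4 it is not a DLT". The catch-all's exclusions include no liver test.

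**Stopping durvalumab.** Section 8.1 says "If any adverse event has occurred, then the treatment schedule will be modified as in Section 8.2", and Section 8.2 says "Durvalumab must be withheld for drug-related toxicities and severe or life-threatening AEs per Table 8.21 below". Table 8.21 requires permanent discontinuation for Grade 3–4 diarrhea/colitis and Grade 3–4 ALT, AST or bilirubin. The summary of changes lists the Grade 3 diarrhea/colitis stop as an FDA-requested edit. Section 8.0 makes the modifications strict for the first two cycles only: "Thereafter, these modifications should be regarded as guidelines to produce mild-to-moderate, but not debilitating, side effects". Its heading sends the reader to an appendix for details. Appendix VII lets durvalumab resume after Grade 3 diarrhea/colitis, or after AST/ALT up to 8x or bilirubin up to 5x ULN, given recovery within 14 days and a completed steroid taper.

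**The concern.** In the accelerated phase each level is judged on one patient, so one DLT call is decisive. A counted event ends single-patient escalation and, if the rest are clean, commits five more patients at that level (two, then three). An uncounted event lets the next patient go up a level. Two readers of Section 7.4.2 could make different calls on the same patient.

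The liver wording matters most because the plan expects events there: Section 1.4.5 says liver enzymes rise in most patients in the first one to two weeks after Y90-RE. The stopping conflict is a patient-safety matter: whether someone who has had Grade 3 colitis or a Grade 3 liver rise may be given durvalumab again. Contact with the Study Chair (7.4.1.2), one-business-day DLT reporting (10.5.5) and assigned attribution (10.2) bring a case to attention quickly. None says which rule decides it.

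**Working it through.** **1. Neutropenia.** Take afebrile Grade 4 lasting d days, then improving a grade. The item applies if d > 5; the exclusion applies if d ≤ 7.

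| d (days) | Item | Exclusion | Result |
|---|---|---|---|
| 5 or fewer | no | yes | not a DLT |
| 6 or 7 | yes | yes | both answers |
| 8 or more | yes | no | DLT |

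**2. Liver rise at cycle 3, gone at cycle 4.** Appendix VII ends Grade 2 at 5x ULN for AST/ALT and 3x for bilirubin, so every row below is above Grade 2.

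| Event | Specific item | Catch-all, read literally |
|---|---|---|
| AST/ALT >8x, or bilirubin >5x | DLT | DLT |
| AST/ALT >5–8x with bilirubin >2x (up to 5x) | expressly not a DLT | no liver exclusion listed |
| AST/ALT >5–8x alone | none | DLT |
| Bilirubin >3–5x alone | none | DLT |

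The cycle 3 to cycle 4 interval is 14 days, or 14 − 10 = 4 to 14 + 10 = 24 days with the ±5-day visit windows. No grade is given for resolution.

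**3. Stopping.**

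| Event | Table 8.21 | Appendix VII |
|---|---|---|
| Grade 3 diarrhea/colitis | permanent stop | resume if Grade ≤1 within 14 days, after taper |
| AST/ALT >5–8x or bilirubin >3–5x | permanent stop | hold; resume if down within 14 days, after taper |
| AST/ALT >3–5x with bilirubin >2–3x, Hy's law criteria met | Grade 2: hold; resumption possible within 2 weeks | permanent stop, except at cycle 3 |

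Cycle 3 starts about day 14 after Y90-RE, and Appendix VII's taper lasts at least 28 days. The week-6 dose is due on day 42, or by day 47 with the window.

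- Latest onset that still permits that dose: 42 − 28 = day 14, or 47 − 28 = day 19.
- If 3 days on full steroids precede the taper: 47 − 28 − 3 = day 16. If 5 days: day 14.
- For the week-4 dose (day 28, or 33): latest onset is day 0, or day 5. That is within cycle 2, where Table 8.21 is strict.

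On schedule, then, only the week-6 dose (levels 3 and 4) is disputed in the first two rows. The plan does not say whether a held dose is skipped or given late. The third row needs no taper under the table: onset on day 28 resolved by day 42 permits the week-6 dose by Table 8.21 and bars it by Appendix VII.

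**4. Patients used.** The plan's own figure first: with no DLT, 3 single patients + 6 at level 4 = 9, matching the 9 evaluable patients in Section 17.3.

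With one disputed event counted at level k and no other DLT, the number before expansion is (k − 1) + 6 + 3(4 − k), plus 3 to bring level 4 to six when k < 4.

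| Counted at level | Before expansion | Left of 18 | Total given level-4 dosing |
|---|---|---|---|
| 1 | 0 + 6 + 9 + 3 = 18 | 0 | 6 |
| 2 | 1 + 6 + 6 + 3 = 16 | 2 | 8 |
| 3 | 2 + 6 + 3 + 3 = 14 | 4 | 10 |
| 4 | 3 + 6 = 9 | 9 | 15 |
| Not counted | 9 | 9 | 15 |

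**5. How often.** The documents give no rate for a disputed event. At an assumed per-patient rate r of 1%, 2%, 5% or 10%, the chance of at least one among four single patients is 1 − (1 − r)^4 = 3.9%, 7.8%, 18.5% or 34.4%.

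**The case against.** **Neutropenia.** The Grade 4 item can be read as controlling, leaving the exclusion to cover afebrile Grade 3 and shorter Grade 4. That is workable, and the disputed band is two days wide. Scheduled blood counts come once per 14-day cycle, so only extra tests would show a 6–7-day duration. Neutropenia is in neither the durvalumab toxicity list (15.17) nor the TheraSphere adverse-event tables. All of this limits the impact; none of it removes the opposing wording.

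**Liver.** A reader might infer that the combined rise is at once a DLT and not a DLT. The documents do not support that: the exemption is explicit and specific, so it most naturally prevails over the lead sentence and catch-all, and Appendix VII shows the same intent at cycle 3. A reader might also infer as settled that a milder isolated rise counts while the worse combined one is forgiven. That is only the literal reading of the catch-all. The separate items at >8x and >5x would be redundant if every isolated Grade 3 rise already counted, which suggests that lower values were not meant to. Immune-related hepatitis also falls under Grade 3 irAE items with their own recovery limits. What stands is that the isolated case is left to inference and resolution is undefined.

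**Stopping.** Sections 8.1 and 8.2 direct use of Table 8.21, Appendix VII is framed as guidance, and in cycles 1–2 the table is strict. So a clash at every cycle is not supported. A Grade 2 hold does not oblige resumption, so obeying Appendix VII's Hy's law stop breaches neither text. Grade 3 colitis is a DLT whichever stopping rule is used, so escalation is unaffected there. From cycle 3, however, both texts are guidance and they differ.

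**Size.** The three patients who fill level 4 receive the same dosing as the expansion cohort, so an expansion of zero is partly a matter of labelling. The immune endpoint pools dose levels (17.3). Both points stand.

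**Conclusion.** The point holds as a lower-priority should-fix. Two conflicts are plain in the current text: afebrile Grade 4 neutropenia at 6–7 days, and Table 8.21 against Appendix VII from cycle 3. The liver DLT wording is a gap rather than a flat contradiction.

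The size is modest. A disputed call on a single patient decides between escalation and 3+3. If counted at level 1, 2 or 3, it moves 9, 7 or 5 patients from expansion into escalation (18, 16 or 14 against 9); at level 4 it changes nothing. These counts assume one disputed event, no other DLT, and six patients required at level 4. A reader might infer a larger trial, or no patients on the top schedule; the total stays 18 and at least 6 still receive level-4 dosing. The re-dosing conflict mainly concerns the week-6 dose at levels 3 and 4.

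Frequency is unknown. Grade 3–4 hyperbilirubinemia in 13% of 531 colorectal patients (1.2.2) shows that high liver values are not rare, but it does not isolate rises that appear at cycle 3 and clear by cycle 4.

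**What to change.** 1. **Neutropenia.** Put one rule among the hematologic items and delete the misplaced exclusion. Afebrile Grade 4 is a DLT if it lasts more than 5 days; afebrile Grade 3 keeps the existing 7-day improvement test; febrile Grade 3–4 always counts. This keeps the stricter limit.
2. **Liver DLT.** Repeat the cycle 3/4 exception in the catch-all with limits: AST/ALT up to 8x and bilirubin up to 5x ULN, resolved to Grade 1 or baseline at the cycle 4 visit. Apply it equally to isolated rises within those limits, so that a milder event is never counted when the combined one is exempt. Make the lead sentence subject to the listed exceptions, so that unlisted Grade 3 or higher events still count.
3. **Diarrhea/colitis.** Change Appendix VII to permanent discontinuation for Grade 3, and state that this applies at all cycles.
4. **Liver stopping rule.** State one action in both places: Table 8.21's permanent stop for Grade 3–4, with either an explicit cycle 3 hold-and-recheck exception or an explicit statement that there is none. Add Appendix VII's Hy's law stop to Table 8.21, so that aligning the texts does not weaken it to a hold.

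The cost is one amendment with FDA and IRB review (Section 10.6), since several of these rules came from FDA requests. The clinical leads must make the cycle 3 liver choice. No patients, visits or tests are added.

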8.0 Dosage Modification Based on Adverse Events (details tabulated in appendix VIII)

Strictly follow the modifications in this table for the first **two** cycles, until individual treatment tolerance can be ascertained. Thereafter, these modifications should be regarded as guidelines to produce mild-to-moderate, but not debilitating, side effects.

8.1 Treatment schedule modifications in patients based on adverse events

Patients will be evaluated by the study team prior to each dose of durvalumab for an adverse event check. Determination will be made if the adverse event is treatment-related (possible, probable or definite), i.e. a toxicity (see Section 10; Adverse event monitoring and reporting). If any adverse event has occurred, then the treatment schedule will be modified as in Section 8.2.

8.2 Treatment schedule modifications for durvalumab

Adverse events (both non-serious and serious) associated with durvalumab exposure may represent an immunologic etiology. These adverse events may occur shortly after the first dose or several months after the last dose of treatment. Durvalumab must be withheld for drug-related toxicities and severe or life-threatening AEs per Table 8.21 below. See Section 9.0 for supportive care guidelines, including use of corticosteroids.

Table 8.21 Dose Modification Guidelines for Drug-Related Adverse Events for Durvalumab			
CTCAE System/Organ/Class	Adverse Event	Grade	Action
Gastrointestinal disorders	Diarrhea or Colitis	2	Hold all protocol treatment until Grade 0-1. If AE does not resolve to Grade 0-1 within 2 weeks, then permanently discontinue all protocol treatment
		3, 4	Permanently discontinue all protocol treatment
Investigations	Alanine aminotransferase increased, Aspartate aminotransferase increased, and blood bilirubin increased	2	Hold all protocol treatment until Grade 0-1. If AE does not resolve to Grade 0-1 within 2 weeks, then permanently discontinue all protocol treatment
		3-4	Permanently discontinue all protocol treatment
Metabolism and nutrition disorders	Glucose intolerance (Type 1 diabetes mellitus [if new onset]) or Hyperglycemia	T1DM or 2-4	Hold all protocol treatment until clinically and metabolically stable.

Table 8.21 Dose Modification Guidelines for Drug-Related Adverse Events for Durvalumab

CTCAE System/Organ/Class	Adverse Event	Grade	Action	
Endocrine disorders	Endocrine disorders-Other, specify: Hypophysitis	2-4	Hold all protocol treatment until Grade 0-1. If AE does not resolve to Grade 0-1 within 2 weeks, then permanently discontinue all protocol treatment	
	Hypothyroidism	2-4	Therapy with durvalumab can be continued while thyroid replacement therapy is instituted	
	Hyperthyroidism	2-3	Hold all protocol treatment until Grade 0-1. If AE does not resolve to Grade 0-1 within 2 weeks, then permanently discontinue all protocol treatment	
		4	Permanently discontinue all protocol treatment	
General disorders and administration site conditions	Infusion related reaction	1, 2	Follow infusion related reaction treatment guidelines (Table 9.21). Hold all protocol treatment until Grade 0-1. If AE does not resolve to Grade 0-1 within 2 weeks, then permanently discontinue all protocol treatment	
		3, 4	Follow infusion related reaction treatment guidelines (Table 9.21). Permanently discontinue all protocol treatment	
Respiratory, thoracic and mediastinal disorders	Pneumonitis	2	Hold all protocol treatment until Grade 0-1 and corticosteroid dose is less than or equal to prednisone 10 mg per day (or equivalent). If AE does not resolve to Grade 0-1 within 2 weeks, then permanently discontinue all protocol treatment	
		3-4	Permanently discontinue all protocol treatment	
Renal and urinary disorders		2	Hold all protocol treatment until Grade 0-1 and corticosteroid dose is less than or equal to prednisone 10 mg per day (or equivalent). If AE does not resolve to Grade 0-1 within 2 weeks, then permanently discontinue all protocol treatment	
		3-4	Permanently discontinue all protocol treatment	
All Other Non-hematologic Events		3	Hold all protocol treatment until Grade 0-1 and corticosteroid dose is less than or equal to prednisone 10 mg per day (or equivalent). If AE does not resolve to Grade 0-1 within 2 weeks, then permanently discontinue all protocol treatment	
		4	Permanently discontinue all protocol treatment	

9.0 Ancillary Treatment/Supportive Care

9.1 Full supportive care

Patients should receive full supportive care while on this study. This includes blood product support, antibiotic treatment, and treatment of other newly diagnosed or concurrent medical conditions. All blood products and concomitant medications such as antidiarrheals, analgesics, and/or antiemetics received from the first day of study treatment administration until 30 days after the final dose will be recorded in the medical records.

9.2 Blood products and growth factors

Blood products and growth factors should be utilized as clinically warranted and following institutional policies and recommendations. The use of growth factors should follow published guidelines of the Journal of Clinical Oncology, Volume 33, No 28 (October 1), 2015: pp. 3199-3212 (WBC growth factors) AND Journal of Clinical Oncology, Volume 28, No 33 (November 20), 2010: pp. 4955-5010 (darbepoetin/epoetin).

9.21 Neutropenia

Prophylactic use of colony-stimulating factors including Granulocyte Colony-Stimulating Factor (G-CSF), PEGylated G-CSF or Granulocyte Macrophage Colony-Stimulating Factor GM-CSF is not allowed in this study. Therapeutic use of G-CSF is allowed in patients with Grade 3-4 febrile neutropenia.

9.22 Anemia

Transfusions and/or erythropoietin may be utilized as clinically indicated for the treatment of anemia but should be clearly noted as concurrent medications.

9.23 Thrombocytopenia

Transfusion of platelets may be used if clinically indicated. ITP should be ruled out before initiation of platelet transfusion.

9.3 Antiemetics

Antiemetics may be used at the discretion of the attending physician.

9.4 Diarrhea

Diarrhea could be managed conservatively with loperamide. The recommended dose of loperamide is 4 mg at first onset, followed by 2 mg every 2-4 hours until diarrhea free (maximum 16 mg/day).

In the event of Grade 3 or 4 diarrhea, the following supportive measures are allowed: hydration, octreotide, and antidiarrheals.

If diarrhea is severe (requiring intravenous rehydration) and/or associated with fever or severe neutropenia (Grade 3 or 4), broad-spectrum antibiotics must be prescribed. Patients with severe diarrhea or any diarrhea associated with severe nausea or vomiting **should be hospitalized** for intravenous hydration and correction of electrolyte imbalances.

9.5 Immunotherapy-related toxicities

Patients should be thoroughly evaluated, and appropriate efforts should be made to rule out neoplastic, infectious, metabolic, toxin, or other etiologic causes of the irAE. Serologic, immunologic, and histologic (biopsy) data, as appropriate, should be used to support an irAE diagnosis. In the absence of a clear alternative etiology, events should be considered potentially immune related.

All toxicities will be graded according to NCI CTCAE, Version 5.

Patients should be monitored for signs and symptoms of immunotherapy-related toxicities, which include but are not limited to the following:

